### **Control group**

Participants will first be considered for enrolment in the posaconazole arm. If there are contraindications to posaconazole, or if enrolment in posaconazole arm has been completed, then subjects will be enrolled in the ketoconazole study, which has a separate IRB-approved protocol (IRB# STUDY00014115). If enrollment in the ketoconazole study is already completed or if the participant is not a candidate for ketoconazole either, then they will be considered for possible candidacy in the control arm.

### **Study drug group**

Participants will be given 12 days' worth of the study drug (pills) and verbally instructed how and when to take them. The prescription bottle will have a label with this information on it as well.

The timing of study drug administration will be based on the scheduled date and time of biopsy or surgery, which will occur within 7-10 days of Visit 1. The latter parameter is based on the drug half-life, as follows:

- Participants will be taking posaconazole as 300mg PO BID in the first day, followed by 300mg PO once daily thereafter.
- The mean elimination half-life of posaconazole is 26-31 hours (product monograph). Therefore, posaconazole will reach steady state at approximately 130-155 hours following the first dose (5 half-lives). As such, we will work backwards from the scheduled date and time of biopsy or surgery such that participants in the posaconazole arm will receive drug for 168-240 hours. The upper range of the dosing (240 hours) is to minimize potentially unnecessary exposure to drug while accounting for variability in half-life measurements.

In order to maintain steady-state concentrations, study drug will be administered at the following times as well:

1. Pre-operatively on the morning of the planned surgical intervention
2. On the morning of postoperative day 1, at 8:00AM +/- 4 hours \*

\*Only if postoperative CT rules out complications and the MDC(s) are correctly positioned.

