##### Study drug group

After biopsy or surgery is completed, patients will have the following as **routine (standard care)**:

- Computed tomography (CT) of the head.
- Neurological examination.

The following will be performed for the **research only**:

- Collection of adverse events experienced during biopsy or surgery as they relate to insertion of microdialysis catheter.

A postoperative CT scan will be performed, as part of the standard of care to rule out immediate postoperative complications such as hemorrhage at catheter tip or misplaced catheter. Other surgical changes will not be considered to be related to the catheter insertion. This will also help confirm the position of the MDC tip: the postoperative CT image is fused with preoperative contrast-enhanced MRI to confirm position within enhancing vs non-enhancing regions. It should be performed after the surgery, prior to the dialysate sample collection the following morning. Per neurosurgical discretion, if the catheter appears malpositioned on imaging or significant tumor bed hemorrhage is present, the microdialysis studies will not be performed. The CT study will be considered abnormal for study purposes if related to the catheter insertion.

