#### **Study drug group**

The following will be performed as **routine (standard care)**:

- Neurological examination.

The following will be performed for the **research only**:

- Patient will take study medication at 8am +/- 4 hours and then study medication will be discontinued.
- Comprehensive Metabolic Panel (which includes electrolytes, renal function and liver function) (approximately 1 teaspoon of blood). Lab values within 1.5x institutional upper limit of normal are acceptable and not considered adverse events.
- Dialysate and blood sample collection.
- Collection of adverse events.

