#### **Microdialysis collection/monitoring**

After the imaging confirms proper placement of the MDC tip, the inlet tubing will be connected to a portable syringe pump to perfuse artificial CSF (Perfusion Fluid CNS, ref. no. P000151, CMA, Solna, Sweden) at a rate of 1.0  $\mu$ l/min. The inlet tubing of the catheter will be connected to a CMA 107 Microdialysis Pump (ref. no. P000127, CMA, Solna Sweden). A microvial will be connected at the end of the outlet tubing to collect perfusate.

Concurrently, a plastic microvial (Ref. No. P000001, CMA, Solna, Sweden) will be placed in the vial holder at the end of the outlet tubing to collect dialysate. This microvial can hold up to 200 $\mu$ L of fluid. It will need to be replaced with a new one every 3 hours. During daytime work week hours, trained research coordinators, in coordination with nursing team will collect dialysate and replace the microvials. At all other times, these tasks will be performed by the study PI, [name].

Dialysate sample collection will begin in the morning of postoperative day 1. If the participant was able to tolerate the AM dose of study drug (study drug group only), sample collection will begin immediately after drug administration. Otherwise, sample collection will begin within the same allotted time period (i.e. 8AM +/- 4 hours). For the control group, sample collection will be at 8 AM +/- 4 hours. The initial sample will be labeled as the 'Time 0' sample. Additional samples will be collected at 15 and 30 minutes, along with 1, 2, 4, 6, 8, and 24 hours after 'Time 0'.

Microvials containing the dialysate should be stored in an ultralow temperature freezer ( $\leq 70^{\circ}\text{C}$ ) until they can be batch analyzed by LC/MS/MS.

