**Schedule of events**

	Visit 1 (Screening and baseline)	Visit 2 (Day 3 +/- 2 days of azole)***^	Visit 3 (morning of and during biopsy or surgery)	Visit 4 (post-op Day 0)	Visit 5 (post-op Day 1)	Visit 6 (post-op Day 2)	Visit 7 (14 days +/- 7 days post-op)
Informed consent process	X						
Demographics +	X						
Medical history +	X						
Neurological Exam +	X			X	X		X
Concomitant medication review +	X		X ^				
Women only: Pregnancy test +, **	X						
12-lead ECG +	X						
MRI Brain +	X*						
Comprehensive Metabolic Panel (which includes electrolytes, renal function and liver function) ^	X	X			X		
CBC ^	X						
Study drug (posaconazole) dispensed ^	X		X#	X#			
Adverse Events (if any)		X	X	X	X		X
Microdialysis catheter placement			X				
Intraoperative blood and tissue collection			X				
CT scan of head +				X			
Dialysate collection					X	X	
Blood sample collection					X	X	
Microdialysis catheter removal						X	

+Performed as routine, standard care (see note about Visit 2) and used for research as well. Any investigations or clinical documentation within 31 days prior to screening are acceptable

\* Previously performed MRI Brain +/- Gadolinium contrast scan within 45 days prior visit 1 will be reviewed as baseline MRI

\*\* Only required for women who, in the investigator's opinion, are of childbearing potential

\*\*\* Only performed for study drug group participants who do not have biopsy or surgery within 3 days. This is a research-only visit and all activities at this visit are for research only.

^Only applicable to those participants in the study drug group.

#As inpatient. Study drug will be dispensed as inpatient on Visit 1 if patient already hospitalized; otherwise it will be outpatient

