##### **7.4.6.3 Preparation and Dispensing**

Once an enrolled subject's biopsy or surgery date is scheduled, subjects will receive an outpatient supply of the posaconazole tablets to take beginning ~130-155 hours prior to biopsy or surgery. Subjects will take six posaconazole 100mg tablets by mouth, once in the morning and once in the evening, on the first day followed by three 100mg tablets by mouth daily. The last dose from the outpatient supply will be taken on the morning of the biopsy or surgery. Subjects should return any study medication remaining when they arrive the day of biopsy or surgery. Post-biopsy or surgery subjects will receive one additional dose of posaconazole 300mg (three 100mg tablets) from the study supply, in the morning after biopsy or surgery. These doses will also be dispensed from a study specific supply. The medication vial should be return to IDS for accountability.

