### Posaconazole Dose Modification for Adverse Reactions

Dose Level	Posaconazole dose
Starting Dose	300 mg once daily
Dose Reduction (33%)	200 mg once daily

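### The protocol disagrees with itself on who receives the postoperative day 1 posaconazole dose, and its dispensing text does not carry through a prior dose reduction

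*Combined protocol and SAP*

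**What the plan says.** All references are to the combined protocol and SAP.

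- **7.2.1 (Study drug group) and 7.4.2 (Treatment Regimen)** carry the same footnote on the day 1 dose: "Only if postoperative CT rules out complications and the MDC(s) are correctly positioned".
- **7.2.5 (Visit 5, Study drug group)** has no condition and no milligram amount: "Patient will take study medication at 8am +/- 4 hours and then study medication will be discontinued".
- **7.4.6.3 (Preparation and Dispensing)** has no condition and fixes the amount: "subjects will receive one additional dose of posaconazole 300mg (three 100mg tablets) from the study supply, in the morning after biopsy or surgery".
- **7.2.4 (Visit 4, Study drug group)** uses the CT to decide on microdialysis, subject to the neurosurgeon's judgement: "if the catheter appears malpositioned on imaging or significant tumor bed hemorrhage is present, the microdialysis studies will not be performed". It does not mention the dose.
- **Microdialysis collection/monitoring (under 7.2.5)** connects the pump once imaging has confirmed tip placement, but speaks of the dose only in terms of tolerance: "If the participant was able to tolerate the AM dose of study drug (study drug group only), sample collection will begin immediately after drug administration".
- **Schedule of events**: the row "Study drug (posaconazole) dispensed" is marked at Visits 1, 3 and 4, the last two as inpatient. Visit 5 is not marked, and no footnote mentions CT or catheter position.
- **18.2 (dose modification table)** gives the reduced level after certain grade 3-4 events as "200 mg once daily".

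**The concern.** The statements select different patients. Under 7.2.1 and 7.4.2, a patient with a CT complication or a misplaced catheter gets no day 1 dose. Under 7.2.5 and 7.4.6.3 as written, the same patient does. No other section settles which applies.

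Two things are at stake. The first is exposure. Section 11.1 says that participants gain no direct benefit, and 7.2.1 itself aims to limit unneeded exposure, so whether a patient with a failed catheter or a bleed takes another dose should not depend on which section is open. The second is adherence. Section 8.2 counts a patient as evaluable only if the drug was taken as the protocol specifies, and here the protocol specifies two things.

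A separate gap concerns the amount. A patient already reduced to 200 mg under 18.2 meets a dispensing instruction that names 300 mg and makes no reference to the reduction.

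**Working it through.** The plan gives no figure to reproduce here, so the check sets the texts side by side and adds two small calculations.

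**1. Who is dosed on day 1, by CT finding**

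| CT and catheter finding | 7.2.1 and 7.4.2 | 7.2.5 and 7.4.6.3, read literally | Microdialysis under 7.2.4 |
|---|---|---|---|
| No complication, catheter well placed | Dose | Dose | Proceeds |
| Catheter misplaced | No dose | Dose | Cancelled |
| Significant tumor bed bleed | No dose | Dose | Cancelled |
| Lesser or other complication, catheter well placed | No dose | Dose | Not cancelled by this text |

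The texts agree in the first row only. In rows two and three, the literal reading doses a patient with no microdialysis. The fourth row arises because the triggers differ: 7.2.1 and 7.4.2 require that the CT exclude complications in general, whereas 7.2.4 names misplacement or a significant bleed and leaves the call to the neurosurgeon. There, the texts differ on whether a dose precedes the 24-hour dialysate curve.

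**2. What the dose would serve once microdialysis is cancelled**

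- The primary outcome in 8.3 is the 24-hour AUC from the catheter. With no dialysate, 0 of 9 time points are available against the 7 of 9 that 8.2 requires, so the patient is not evaluable for the primary endpoint and is replaced.
- The tumor tissue measures in 8.3 come from the operation, before this dose.
- The lactate and pyruvate profiles in 8.3 also need the catheter.
- The tolerability endpoint in 1.3 concerns preoperative dosing.
- Plasma collection under 7.2.5 is not expressly cancelled, and 9.2 lists blood drug concentration among the data reviewed, but 8.3 defines no plasma endpoint.

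**3. Dose amount**

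- Dispensing text: 3 × 100 mg = 300 mg, consistent with the standard daily dose in 7.2.1 and 7.4.2.
- Reduced level in 18.2: 200 mg. Then 300 / 200 = 1.5, so the dispensing text names 1.5 times the reduced dose.
- 18.2 is also unclear in itself. Its text speaks of going down to 33% of the scheduled dose and gives 200 mg, yet 200 / 300 = 67%. The figure of 200 mg is a reduction *by* 100 / 300 = 33%.

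**4. Illustration of how often the texts would diverge**

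The documents give no rate p of an abnormal CT or misplaced catheter, so p is assumed, equal and independent across five operated study-drug patients. The chance that at least one falls where the texts differ is 1 − (1 − p)^5:

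- p = 0.05: 1 − 0.95^5 = 0.226, or 23%
- p = 0.10: 1 − 0.90^5 = 0.410, or 41%
- p = 0.20: 1 − 0.80^5 = 0.672, or 67%

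Replacement of non-evaluable patients (8.2) raises the number operated on and so raises these values.

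**The case against.** The best reply is that silence is not contradiction. The condition appears twice in identical words, once in the section that defines the regimen, and nothing in 7.2.5 or 7.4.6.3 says that the dose is given whatever the CT shows. The Visit 5 list also includes dialysate collection without a condition, although 7.2.4 may have cancelled it, so the list may simply describe a patient who is proceeding. Section 3.3.1 lets the physician stop treatment in the patient's interest. The patient has already had 168 to 240 hours of drug and enters any safety analysis with or without one more dose.

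Much of this stands. A careful reader can carry the footnote into Visit 5, and the added exposure is a single dose. It does not dispose of the point. The dispensing section is a separate instruction to supply the dose and refers to no condition. Even with the footnote carried over, 7.2.4 uses a different trigger, and the schedule does not help.

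Some stronger readings are tempting but not supported:

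- *A reader might infer that 7.4.6.3 also reaches operated patients found not to have high-grade glioma.* The intra-operative procedure makes them screen failures with no catheter, and the off-study criteria in 8.3 list pathology not consistent with glioma.
- *A reader might infer that the dispensing amount differs from 7.2.1 and 7.4.2.* Those sections also state 300 mg daily. The only conflict over amount is with 18.2.
- *A reader might infer that the dose serves no research purpose once microdialysis is cancelled.* Plasma sampling may continue. The supported statement is that section 8 defines no endpoint that needs the dose.
- *A reader might infer that staff follow 7.2.5 and 7.4.6.3 rather than 7.2.1 and 7.4.2.* The documents do not rank these sections.

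**Conclusion.** The inconsistency is real and should be corrected. The protocol states the day 1 dose conditionally in two places and unconditionally in two others, words the CT trigger differently in 7.2.4, and offers no text that settles who is dosed. A patient whose microdialysis is cancelled is dosed under one reading and not under the other, and contributes nothing to the primary endpoint either way. The fixed 300 mg against the reduced 200 mg is a second, narrower gap.

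The size is modest: one dose per affected patient, and a factor of 1.5 for anyone already on the reduced dose. The 23% to 67% range is illustrative only. It rests on assumed rates and measures how often the texts would part company for at least one of five patients. A reader might take it as the chance of a dosing error, but that would also require staff to overlook the footnote, and the documents say nothing about how likely that is. The point does not bear on the choice of sample size or the AUC method, and it implies no view on which rule or dose is right.

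**What to change.** Reconcile 7.2.1, 7.2.4, 7.2.5 (including its microdialysis text), 7.4.2, 7.4.6.3, the schedule of events and 18.2. State once:

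- who receives the day 1 dose, explicitly covering patients whose microdialysis is cancelled;
- on what CT or catheter trigger, if any, in the same terms wherever it appears;
- how a prior dose reduction carries through to this dose, with the percentage and milligram wording in 18.2 made to agree.

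Cross-reference that statement in 7.2.5, 7.4.6.3 and the schedule of events, and make the dispensing row show the visit to which the dose belongs. The choice of rule and dose rests with the investigators.

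The cost is a wording amendment to a handful of sections, with no added procedure, visit or patient.

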### **Concurrent treatment considerations and restrictions:**

- Patients with HGGs will often have peri-tumoral edema for which corticosteroids are often effective. Given the influence of posaconazole on suppressing adrenal function, this exogenous steroid will also help to replace affected adrenal function and, therefore, concomitant use will be allowed. The corticosteroid of choice is dexamethasone, at a dose of 4mg PO QID. Stress dosing at time of biopsy or surgery will be at discretion of surgical and anesthesia teams.
- Due to the possible adverse effect of corticosteroids on the protective gastric lining, patients are often required to concomitantly take H2 blockers such as ranitidine (150mg po BID) during their course of corticosteroids. This could adversely affect the absorption of posaconazole. Therefore, patients will take posaconazole at least 2 hours before taking ranitidine.
- Other drugs that decrease the amount of stomach acid include over-the-counter antacids, proton pump inhibitors, sucralfate. Drugs that slow down gut movement

include anticholinergics such as dicyclomine, propantheline. Patients taking either class of drugs will be advised to take posaconazole at least 2 hours before.

- Patients will be asked to avoid alcohol for at least 3 days after finishing the drug.

### **7.2.2 Visit 2 (3 days +/- 2 days after starting the study drug)**

**This visit is ONLY for the study drug arm.** Participants will return to the clinic for a **research-only visit**. At this visit, the following will be performed:

- Collection of adverse events.
- A 12-lead ECG to rule out QTc prolongation
- Comprehensive Metabolic Panel (which includes electrolytes, renal function and liver function). Lab values within 1.5x institutional upper limit of normal are acceptable and not considered adverse events.

### **7.2.3 Visit 3 (Day of biopsy or surgery)**

#### **Control group**

The following will be performed for the **research only**:

- Collection of adverse events.

#### **Study drug group**

Participants will bring their study drug prescription bottle with them.

The following will be performed for the **research only**:

- Patient will take study drug at 8am (+/- 4 hours)
- Collection of adverse events.
- Study Medication Compliance and checking of medication diary.
- Record date and time of study medication of this day for the research records and to confirm it was taken in the morning.
- If HGG diagnosis verified, record date and time of tissue sample collection, blood sample collection and microdialysis catheter placement.

#### **Intra-operative procedure**

##### **Assessments common to both control and study drug groups**

After surgical resection, frozen pathology will be reviewed to verify the diagnosis of HGG. Once pathology has been verified, and it is determined there is adequate tissue for clinical diagnosis, we will take our research sample will be taken and prepared for assessment of intra-tumoral drug concentration (study drug arm only) and assessment of HK2 activity, downstream glycolysis metabolites, tumor cell proliferation, and angiogenesis.

Where an open surgical resection has been planned, one (1) tissue sample will be from the center of the tumor and one (1) from the tumor capsule and snap-frozen immediately in the operating room (<15 minutes). No individual sample will be greater than 1cm x 1cm. These will then be divided for individual research-specific analyses.

As noted below for postoperative plasma collection schedule, blood samples will be obtained at the time of tumor sampling as well to determine and compare tumor: blood drug concentration ratios. The exact time of tumor resection and blood sampling will be recorded.

For patients in whom the intraoperative diagnosis is not consistent with HGG, no additional blood will be drawn and the patient will not be able to continue study and will be considered a

screen fail. Furthermore, no MDC will be inserted. Surgical procedures necessary for the management for the particular diagnosis will be undertaken as per standard protocol for the surgeon.

Upon satisfactory resection of tumor bulk, the neurosurgeon will place two CMA 70 MDCs with Gold Tip - (ref. no. P000050, CMA, Solna, Sweden) with a membrane length of 10mm, and shaft length 100mm - in accordance with pre-op MRI. For patients with a subtotal resection of enhancing tumor, one MDC will be placed in a contrast enhancing area of the tumor and another will be placed in a non-contrast enhancing region (normal brain) within 5mm of tumor resection cavity. For patients with a complete resection of contrast-enhancing tumor, only one MDC will be placed in the non-enhancing tumor resection boundary, within 5mm of resection cavity. Ultimately, the decision on number of catheters inserted will be at the discretion of the surgeon. Upon completion of the surgical procedure, the wound will then be irrigated and closed in standard fashion and lastly the catheter will be anchored to the scalp with sutures and sterile dressings.

#### 7.2.4 Visit 4 (Post-operative, Day 0)

##### Control group

After biopsy or surgery is completed, patients will have the following as **routine (standard care)**:

- Computed tomography (CT) of the head.
- Neurological examination.

The following will be performed for the **research only**:

- Collection of adverse events experienced during biopsy or surgery as they relate to insertion of microdialysis catheter, if any.

##### Study drug group

After biopsy or surgery is completed, patients will have the following as **routine (standard care)**:

- Computed tomography (CT) of the head.
- Neurological examination.

The following will be performed for the **research only**:

- Collection of adverse events experienced during biopsy or surgery as they relate to insertion of microdialysis catheter.

A postoperative CT scan will be performed, as part of the standard of care to rule out immediate postoperative complications such as hemorrhage at catheter tip or misplaced catheter. Other surgical changes will not be considered to be related to the catheter insertion. This will also help confirm the position of the MDC tip: the postoperative CT image is fused with preoperative contrast-enhanced MRI to confirm position within enhancing vs non-enhancing regions. It should be performed after the surgery, prior to the dialysate sample collection the following morning. Per neurosurgical discretion, if the catheter appears malpositioned on imaging or significant tumor bed hemorrhage is present, the microdialysis studies will not be performed. The CT study will be considered abnormal for study purposes if related to the catheter insertion.

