### **Secondary Objectives**

- Tolerability: Adverse experiences observed over the 7-21 days of protocol follow-up will be characterized in CTCAE v5.0. Frequency and severity of AEs according to body system and severity criteria will be described. In addition, frequency of grade 3 or 4 adverse events will be described separately. Causality will also be noted. Laboratory assessments will also be described according to the NCI CTCAE, V 5.0 criteria, with separate descriptions for grade 3 or 4 laboratory abnormalities. Clinically significant laboratory abnormalities will be described as well.
- Pharmacodynamics: Descriptive statistics, using means/ median, will be used to report drug effect on:
  - a) HK2 activity in resected tumor tissue
  - b) Concentration of downstream glycolysis metabolites in resected tumor tissue

- c) Tumor cell proliferation, cell death, and angiogenesis in resected tumor tissue
- d) Concentration vs time profile of lactate and pyruvate, based on MDC studies, in relation to the concentration vs time profile of posaconazole.

\*\* The above values will be compared to levels in the control arm.

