## **9.0 Data and Safety Monitoring Plan**

### **9.1 Periodic evaluation of data**

To monitor safety throughout the course of the study, every effort will be made to remain alert to possible AEs/SAEs. If an AE/SAE occurs, the first concern should be for the safety of the subject. If necessary, appropriate medical intervention will be provided. At the signing of the written consent form, each subject or his/her legally authorized representative and/or main caregiver must be given the names and telephone numbers of study site staff for reporting AEs/SAEs and medical emergencies. In this study, any AE/SAE experienced by the subject between the time of first dose of study treatment and 24 hours after the last dose will be recorded on the electronic case report form, regardless of the severity of the event or its relationship to study treatment. During study treatment and visit after 14 days, the research team will assess the subject for AEs and will record any new AEs/SAEs or updates to previously reported AEs on the electronic case report form.

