## 18.2 Recording of Adverse Events

Subjects will be encouraged to spontaneously report any AE. Study personnel will ask open-ended questions to obtain information about AEs at every visit. Date and time of onset and resolution (if applicable) of the AE will be documented. All AEs occurring after the initiation of the study treatment (treatment emergent adverse events) will be reported, including events present at baseline that worsened during the study.

Safety will be assessed by the investigator in the form of evaluation of adverse events and clinical laboratory results and derived as data sets and frequency methods, recorded for this study. AEs by severity and causality as described below:

- Laboratory evaluations including liver function tests. Laboratory values within 1.5x the institutional upper limit of normal are considered acceptable and not as AEs

To monitor any risk of increased surgical complications associated with posaconazole, the treating surgeons will make a Note-to-File recording any unexpected events that occurred during surgery.

Patients unable to tolerate posaconazole due to AE grade 3-4 (hepatic, gastroenterological, and/or renal toxicity) will have a dose reduction. Posaconazole will be reduced to 33% of schedule dose (200 mg per dose, see table below). If the AE does not resolve within 24 hours, it will be discontinued. However, tumor tissue will still be collected and analyzed.

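### Day 0 adverse event collection is limited to catheter insertion, against the plan's own all-event rules, so the surgical-complication aim has no secured control comparator

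*Combined protocol and SAP*

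**What the plan says.** Section 7.2.4 gives the research tasks for Visit 4, the day of surgery. In the study drug group the adverse event task is "Collection of adverse events experienced during biopsy or surgery as they relate to insertion of microdialysis catheter". In the control group it is "Collection of adverse events experienced during biopsy or surgery as they relate to insertion of microdialysis catheter, if any". The text on the postoperative CT, under the study drug group, adds: "Other surgical changes will not be considered to be related to the catheter insertion".

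The general rules are wider. Section 9.1 sets a window that opens at the first dose and closes a day after the final one. It says that events inside this window "will be recorded on the electronic case report form, regardless of the severity of the event or its relationship to study treatment". Section 18.2 has staff ask open questions about adverse events at every visit and reports all events arising after study treatment begins. The schedule of events marks adverse events at Visit 4 with no limiting footnote.

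Section 18.2 also sets a surgical aim: "To monitor any risk of increased surgical complications associated with posaconazole". The tool that it names for this aim is a written record: "the treating surgeons will make a Note-to-File recording any unexpected events that occurred during surgery". Section 8.3 describes adverse experiences over follow-up by CTCAE v5.0. Tolerability is the first secondary endpoint in section 1.3.

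**The concern.** The Visit 4 instruction uses cause as a condition of entry. A complication of the resection that nobody attributes to the catheter falls outside it, on the day when drug, anaesthesia and resection act together. Staff who follow section 7.2.4 and staff who follow section 9.1 would record different data from the same patient.

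The surgical aim makes this matter more. Whether complications are increased can be judged only against patients who had the operation without the drug. That needs the same events recorded in the same way in both arms, including expected complications that may simply become more frequent. If capture differs between arms, the comparison can err in either direction: events missed in treated patients flatter the drug, and events missed in controls count against it.

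**Working it through.** The plan gives no figure on this point, so the check sets the instructions side by side and then asks whom each one reaches.

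**1. Scope of each instruction around surgery**

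| Place | Reaches | Scope |
|---|---|---|
| 7.2.3, Visit 3 | Both groups | No filter; the schedule of events defines this visit as including the operation |
| 7.2.4, Visit 4 | Both groups | Events related to catheter insertion |
| 7.2.5, Visit 5 | Both groups | No filter |
| Schedule of events, Visit 4 | Both groups | Marked, no restriction |
| 9.1 | First dose to 24 hours after last dose | Any severity, any relationship, on the eCRF |
| 18.2, reporting rule | From start of study treatment | All events |
| 18.2, questioning | Every visit | Open-ended |
| 8.3, tolerability | Adverse experiences over follow-up | Surgical events not excluded |

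Visit 4 is the only row with a filter by cause.

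**2. Does the section 9.1 window cover surgery in dosed patients?** It closes at last dose + 24 hours.

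- Postoperative day 1 dose given at 8:00 +/- 4 hours: the window closes on day 2 at 8:00 +/- 4 hours, that is 04:00 to 12:00. Surgery and all of Day 0 are inside.
- Day 1 dose withheld, last dose on the morning of surgery (7.2.1, 7.2.3, 7.4.6.3): it closes on day 1 between 04:00 and 12:00. Surgery and Day 0 are still inside.
- Section 7.4.2 words the preoperative dose as falling on the morning prior to surgery. If that means the day before and the day 1 dose is withheld, the window closes on the morning of surgery, possibly before the operation. These sections must be reconciled.
- Dosing stopped earlier: the eCRF window can close before surgery, but the section 18.2 reporting rule has no stated end and still applies.

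So a dosed patient's surgical event should normally be recorded despite the Visit 4 wording.

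**3. What reaches controls?** Controls have no first dose and no start of treatment, so neither the section 9.1 window nor the section 18.2 reporting rule is defined for them. The adverse event definition in 18.1 refers to use of the drug, and the safety set in 3.3.1 is defined by receipt of a dose. What remains is the visit-level wording, the schedule row and the open questions. On Day 0 the most specific of these is catheter-only.

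**4. Where does the surgeon's note go?** It covers unexpected events, so an expected complication that becomes more frequent is outside it. No section states that the note is graded, transcribed to the CRF or tabulated. Section 9.2 lists CTCAE adverse events as the clinical safety data reviewed. In section 8.3 the sentence on comparison with controls follows the pharmacodynamic list and speaks of levels, so it does not clearly include adverse events.

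**5. Size, as illustration only.** With n = 5 and exact (Clopper-Pearson) 95% limits:

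- 1/5 = 20%. Lower limit 1 - 0.975^(1/5) = 0.005. The upper limit solves (1-p)^5 + 5p(1-p)^4 = 0.025, giving p = 0.716.
- 0/5 = 0%. Upper limit 1 - 0.025^(1/5) = 0.522.

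One missed event changes the report from 20% (0.5% to 72%) to 0% (0% to 52%). If one such event occurs in each arm and only the control event is missed, a true 1/5 versus 1/5 is reported as 1/5 versus 0/5.

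**The case against.** A reader might infer that surgical complications never enter the tolerability analysis, or that comparison with controls is impossible. The documents do not support that. Visit 3 takes in the operation and collects adverse events without a filter in both arms, and Visit 5 the next morning does the same. Sections 9.1 and 18.2 require all events in dosed patients, and section 8.3 excludes none of them. Section 18.3 has the investigator decide whether abnormal test findings are adverse events. Section 19.1.1 provides source document verification, and 19.1.2 has the PI and the monitor check the entries. The Note-to-File sits in the section that requires all events to be reported and is not said to replace the form. The Visit 4 line can be read as an added device prompt. The CT text calls the scan abnormal for study purposes if the finding relates to the catheter; it does not say only if.

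All of this stands against a claim of exclusion. It does not remove the conflict: the Visit 4 bullet is worded as the task itself, and the checks in 19.1 confirm entries without saying which rule decides what should be entered.

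Two further objections also stand in part. The five-patient arithmetic would fit any missed event. And five versus five, non-randomised, with controls reached only after the posaconazole arm and the ketoconazole study have been considered, can hardly establish increased risk. Both limit the stakes, but a descriptive comparison still needs even capture.

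**Conclusion.** The Visit 4 instruction contradicts the schedule of events and sections 9.1 and 18.2. For dosed patients the consequence is a risk of under-capture and inconsistent capture. For controls the gap is larger, because the general recording rules are tied to treatment and the Day 0 wording is catheter-only. The aim of monitoring increased surgical complications therefore has no secured comparator, and its named tool is limited to unexpected events without a stated route into the adverse event data.

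The size cannot be estimated: the plan gives no expected complication rate, and the 20-point shift assumes exactly one missed event. The conclusion assumes that no CRF guideline outside these documents already settles Day 0 scope or the control window. The endpoint is secondary and descriptive, so this is a correction worth making before data collection and not a threat to the primary pharmacokinetic result.

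A reader might also infer that deaths go unreported because "frequency of grade 3 or 4 adverse events will be described separately". They do not: the general description of severity in section 8.3 already covers grade 5.

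**What to change.** 1. Reconcile section 7.2.4 with the schedule of events and sections 9.1 and 18.2: collect all adverse events at Visit 4 in both groups, and record relationship to catheter, drug or surgery as an attribute of each event.
2. Define an adverse event window for controls, anchored to an event other than dosing, such as consent or surgery, and running through Visit 7. State the control denominator for safety tables.
3. Enter intraoperative complications, expected or not, as CTCAE v5.0-graded adverse events on the CRF for every participant in both arms. A surgeon's note may remain as a source document.
4. In section 8.3, tabulate intraoperative and Day 0 events by arm.
5. Optional wording: extend the separate display to grades 3 to 5.

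The cost is one CRF item and amendment wording. The drawback is that more expected surgical events will be recorded in both arms; the relationship field lets them be shown separately. Treatment and sample collection do not change.
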